6.20.7.8. Non-Evaluable

In a subject who does not have evidence of PD, no images or inadequate or missing images indicates a response status of NE. In a subject with LPL/WM, missing on-study monoclonal IgM concentration by SPEP or total serum IgM quantitation by nephelometry will result in response status of NE. If the baseline IgM value is missing, IgM will not be considered for the on-study disease assessments.

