3.2. Treatment Regimen

Initially subjects with iNHL and NHL will receive treatment with 800 mg GS-9973 BID (under fasted conditions (as defined in Section 5.5.10)). As of protocol amendment 8, subjects receiving GS-9973 MM formulation will be transitioned to the GS-9973 SDD formulation (Section 5.3.5).

GS-9973 SDD doses of 100, 200 or 400 mg given BID will be studied in the additional cohorts. A specific dosing regimen will be selected based upon the emerging pharmacodynamic, pharmacokinetic and anti-tumor data from the CLL dose ranging subjects and all cohorts will be transition to the dose level of GS-9973 SDD.

Initially subjects in the CLL prior BTK inhibitor exposure or CLL prior PI3K inhibitor exposure cohorts will receive GS-9973 SDD 400 mg twice daily (BID). Subjects in the CLL dose ranging cohorts will receive the GS-9973 SDD at the dose level assigned in the randomization.

For study purposes, a cycle is considered to be 28 days. In the absence of toxicity requiring a drug holiday (as defined in Section 8.10), dosing will be continuous without interruption. Subjects will have evaluations for safety and provide blood for drug levels and pharmacodynamic monitoring prior to starting treatment and then 1.5 hours thereafter per the following schedule: at initial dose, weekly during Cycle 1, every 2 weeks during Cycle 2, and then once each cycle thereafter. Additional PK samples will be collected at 4 hours after dosing on Cycle 1 Day 1 and Cycle 1 Day 8. Subjects will undergo a radiographic assessment to determine their tumor response to treatment every 8 weeks during the first 24 weeks and then every 12 weeks thereafter for all diagnoses, except LPL/WM who did not have measurable disease at the time of the study and who are not suspected to have measurable disease at the time of progression. For those LPL/WM patients, the reassessments will consist of bone marrow evaluation, serum monoclonal IgM, done by same technique as used in screening, and cryoglobulin. A bone marrow must be done at PD if that is the only source of the PD and at CR to confirm the CR to determine their tumor response to treatment every 8 weeks during the first 24 weeks and then every 12 weeks thereafter.

Treatment with GS-9973 or GS-9973 SDD may continue in the absence of disease progression or unacceptable toxicity.

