6.5. Assessment of Tumor Response

The procedures to assess tumor response will be conducted every 8 weeks during the first 24 weeks on study and then every 12 weeks up to 72 weeks, regardless of cycle number and regardless of any dose interruptions (ie, Weeks 8, 16, 24, 36, 48, 60, 72, etc). Tumor assessments must be done any time during the specified week (+/-3 days around the week). Therefore there is a 13-day window to conduct tumor assessments that begins 3 days prior to the start of the last week of the corresponding 28-day cycle and ends 3 days after the last day of that same corresponding cycle. The description of the assessments to be conducted are detailed in Section [6.12](#) and outlined in the Study Procedures Table in [Appendix 2](#).

A bone marrow biopsy and aspirate will be collected for all subjects who achieve a CR for confirmatory purpose. For LPL/WM without adenopathy and CLL subjects a bone marrow biopsy/aspirate will be collected to confirm a PD if based only upon declines in the platelet count and/or hemoglobin for CLL subjects or rise in Serum monoclonal IgM in LPL/WM. For all LPL/WM patients who achieve CR or PD and are not evaluable by radiological criteria require confirmation by bone marrow evaluation. If the subject does not otherwise meet criteria for CR or if the nature of PD does not require bone marrow confirmations, it is not necessary to obtain a bone marrow biopsy/aspirate (See Sections [6.20](#) and [6.21](#)).

ONLY for subjects with LPL/WM, an evaluation of serum monoclonal IgM by both SPEP and IFE will be conducted including cryoglobulin testing (LPL/WM enrollment limited to those sites which have cryoglobulin analysis capabilities). Serum monoclonal IgM as assessed by SPEP will only be considered if baseline total serum IgM quantitation by nephelometry is not available.

This procedure should be conducted on the Day 1 visit occurring during the week window allotted for tumor response assessments. LPL/WM subjects who do not have lymphadenopathy on their screening CT/MRI evaluations are not required to have repeated scans for tumor assessment unless clinically indicated, but all subjects in this subset will require BM evaluations for suspected PD or CR assessments.

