6.12. Tumor Imaging (CT or MRI)

CT or MRI scans will be obtained to document sites of disease, identify target lesions as described in Section 6.20.4 and 6.21.4 and to assess response and disease progression. CT scan is the preferred method for radiographic tumor assessment. MRI scanning may be used at the investigator's discretion in subjects for whom this may be a preferred alternative to CT scanning; however, if MRI is performed, a non-contrast CT of the chest should also be performed. Contrast-enhanced scanning is preferred, but iodine-containing or gadolinium contrast material may be omitted in subjects for whom use of a contrast agent would be medically contraindicated. Imaging of the neck, chest, abdomen and pelvis by CT scan (with contrast) or MRI will be performed as part of the Screening Procedures (or within 5 weeks before Dosing Day 1 if the scan was performed as part of standard medical practice). Imaging will then occur every 8 weeks from Cycle 1 Day 1 date during the first 24 weeks of the study and then every 12 weeks thereafter until week 72 regardless of any dose interruptions. After week 72 scans will occur at least every 6 months (\pm 4 weeks). At all timepoints after Screening, imaging of the chest, abdomen, and pelvis will be required. Imaging of the neck is required at each follow-up time point if the neck scan was positive at baseline or if palpable neck lymphadenopathy appears during the course of the study.

The imaging procedure and specification (eg, the same contrast agent, slice thickness, etc.) used to define measurable target and non-target lesions must be used throughout the study for each subject. Any subject with symptoms suggestive of disease progression should be evaluated for tumor response at the time the symptoms occur. Tumor burden will be characterized at baseline and subsequent response assessments will be carried out according to Section 3. Scans need to be of high quality and digitalized in the Digital Imaging and Communication in Medicine (DICOM) format to be collected and to allow for reading by the IRC (see Section 9.4).

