6.20.2. Method of Assessment

In addition to clinical examination, imaging-based evaluation will be used in this study in all subjects enrolled. CT scan is the preferred method for radiographic tumor assessment. MRI scanning may be used at the investigator's discretion in subjects for whom this may be a preferred alternative to CT scanning. Contrast-enhanced scanning is preferred, but iodine-containing or gadolinium contrast material may be omitted in subjects for whom use of a contrast agent would be medically contraindicated. PET scanning can be performed as appropriate. As appropriate, study drug dosing delays, bone marrow aspirate/biopsy information (eg, for confirmation of CR) and biopsy information (eg, for documentation of disease transformation to an aggressive histology) will also be considered. For LPL/WM, quantitative monoclonal IgM protein as assessed by SPEP and IFE will be considered. Clinical palpation, chest x-ray, ultrasound, endoscopy, laparoscopy, radionuclide scans, or tumor markers will not be considered for response assessment.

For radiographic evaluations, the same method of assessment and the same technique (eg, scan type, scanner, subject position, dose of contrast, injection/scan interval) should be used to characterize each identified and reported lesion at baseline and during study treatment and follow-up. Furthermore, the use of IV contrast should be consistent across timepoints. In the event that the screening/baseline CT scan of the neck, chest, abdomen and pelvis is performed without IV contrast, the follow-up time points should also be performed without IV contrast. CT or MRI of the neck, chest, abdomen, and pelvis should be performed with cuts of ≤ 1.0 cm (ideally ≤ 0.5 cm) in slice thickness contiguously. At Screening CT or MRI of neck, chest, abdomen, and pelvis is required. At all timepoints after Screening imaging of the chest, abdomen, and pelvis will be required. Imaging of the neck is required at each follow-up time point if the neck scan was positive at baseline or if palpable neck lymphadenopathy appears during the course of the study.

All relevant clinical and radiographic information required to make each tumor status assessment must be made available for source verification and for submission to the IRC (see Section 9.4).

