6.20.7. Definitions of Tumor Response and Progression

6.20.7.1. Best Overall Response

Responses will be categorized as CR, PR, SD, or PD. In addition, a response category of not evaluable (NE) is provided for situations in which there is inadequate information to otherwise categorize response status. A response category of no disease (ND) is included for situations in which there is no evidence of tumor either at baseline or on treatment.

The best overall response will be determined. The best overall response is the best response recorded from the start of treatment until progressive disease/recurrence (taking as reference for PD the smallest measurements recorded since treatment started). Subjects with NE or ND will be counted as failures in the analyses of tumor response.

- A radiological best overall response of CR, PR, SD, PD, NE and ND is allowed.
- Neither a PR nor an SD designation may follow a CR. Once a CR is observed, the subject will continue to be considered to have CR status until the criteria for PD are met.
- An SD designation may not follow a PR designation. In cases where a subject has an apparent worsening of lesions following a PR, the subject will continue to be considered to have PR status until the criteria for PD are met.

- Subjects will be defined NE if there is no adequate on-treatment radiological response assessment. NOTE: These subjects will be counted as failures in the primary analysis of tumor response data.
- For subjects with LPL/WM, a minor response and very good partial response is allowed based on a reduction of monoclonal IgM concentrations.

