- Pseudo-progression characterized by a paradoxical rise in serum IgM followed by a delayed response has been recognized early in the course of treatment of subjects with WM/LPL treated with chemotherapy and immunotherapy. The time to responses following pseudo-progression may be delayed for >4 months in some cases. Expert opinion specifically cautions against premature disease response assessment in LPL/Waldenström's therefore unless there is compelling clinical and objective data of progression all subjects should have at least 4 months of treatment before an assessment of PD is made. When assessing for progression a bone marrow biopsy and/or CT scan should be used in conjunction with serum IgM levels to assess disease burden. Criteria for progression based on serum IgM include, a $\geq 25\%$ increase from the nadir in either monoclonal IgM concentration by SPEP or total serum IgM quantitation by nephelometry (with confirmation by a repeat measurement) at least 6 weeks apart.
- An absolute increase of at least 0.5 gram/dL is required to define progression with confirmation at least 6 weeks apart.

Note: If there is uncertainty regarding whether there is true progression, the subject may continue study treatment and remain under close observation (eg, evaluated at 4-week intervals). If subsequent evaluations suggest that the subject is experiencing progression, then the date of progression should be the timepoint at which progression was first identified. A single PD determination followed by a determination that indicates either no change or improvement in disease prior to the single PD observation will not be considered PD.

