6.20.7.9. No Disease

In a subject who does not have evidence of PD, the occurrence of the following condition indicates a response status of ND:

- No index disease noted at baseline or on-treatment.
- No non-index disease noted at baseline or on-treatment.
- Enlargement of the liver or spleen is absent both at baseline and on-treatment
- In a subject with LPL/WM, the additional requirement that serum monoclonal IgM protein as assessed by SPEP is absent at both baseline and on-study.

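### LPL/WM subjects excused from repeat scans are rated non-evaluable by the protocol's response rules, and the PR rule cannot be met without an index lesion

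*Protocol*

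**What the plan says.** **Scan waiver.** Protocol 6.5 states that LPL/WM subjects without lymphadenopathy at screening "are not required to have repeated scans for tumor assessment unless clinically indicated". Protocol 3.2 takes LPL/WM subjects without measurable disease out of the radiographic schedule: "For those LPL/WM patients, the reassessments will consist of bone marrow evaluation, serum monoclonal IgM", plus cryoglobulin.

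**Imaging rules with no LPL/WM exemption.** Protocol 6.12: "At all timepoints after Screening, imaging of the chest, abdomen, and pelvis will be required". Protocol 6.20.2 ("At all timepoints after Screening imaging of the chest, abdomen, and pelvis will be required") and Appendix 2 note h say the same.

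**NE rules with no LPL/WM exemption.** Protocol 6.20.7.8: "no images or inadequate or missing images indicates a response status of NE". Its next sentence concerns LPL/WM and adds missing IgM as a second route to NE. Protocol 6.20.7.1: "Subjects will be defined NE if there is no adequate on-treatment radiological response assessment", counted as failures.

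**Signs that an IgM route was meant.** Protocol 6.5 foresees LPL/WM subjects who cannot be evaluated radiologically reaching CR or PD with marrow confirmation. Protocol 6.20.7.1 allows MR and VGPR on IgM. Protocol 6.20.7.9 makes ND for LPL/WM subject to "the additional requirement that serum monoclonal IgM protein as assessed by SPEP is absent at both baseline and on-study".

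**SAP.** Appendix 2 lists NE as not adequate. Table 13-1, step 2, censors a living subject with no adequate post-baseline assessment on Study Day 1. Section 6.2.1 counts a subject with inadequate on-study tumor information as a non-responder.

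**The concern.** A subject can follow the waiver in 6.5 exactly, have every scheduled IgM measured, stay progression-free, and still have NE at every visit. PD is on the SAP's list of adequate assessments, so a progressor found by IgM and marrow can be an event while a progression-free subject leaves the risk set on Day 1. That censoring depends on outcome and pulls the Week 24 PFS estimate down.

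Setting the NE rule aside exposes a second defect. The LPL/WM version of PR needs a decrease in index-lesion SPD, which cannot happen when there is no index lesion. A larger IgM fall may then not count as a response while a smaller one does.

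The primary endpoint and ORR for these subjects therefore depend on a reading that the documents leave open, and that might be chosen after data have been seen.

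**Working it through.** The plan states no figure on this point, so there is none to reproduce.

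**Step 1. Does any text override the NE rule?** The waiver (3.2, 6.5) concerns which procedures are done. The NE text (6.20.7.1, 6.20.7.8) concerns status and contains no exception. The passages that suggest an IgM route show intent but do not say that an unscanned visit is evaluable.

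**Step 2. Consequence under the SAP.** NE at all visits means no adequate post-baseline assessment, so a living subject is censored on Study Day 1 and is an ORR non-responder. A death on or before the second scheduled assessment, without other anti-cancer therapy, is still an event.

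**Step 3. Response rules with NE waived.** Assume no index lesion, no new disease, no PD, and CR not met.

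| IgM fall | Result under 6.20.7.3 to 6.20.7.6 |
|---|---|
| under 25% | SD |
| 25% to under 50% | MR, counted in ORR |
| 50% to 90% | not PR (no SPD decrease possible), not MR (capped below 50%) |
| over 90% | VGPR only if the other CR criteria are met; otherwise as the row above |

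With a shrinking index lesion, a fall of 50% or more is PR. The CR criteria in 6.20.7.2 include spleen and liver size judged by imaging, and VGPR inherits this. An unscanned subject strictly reaches neither, although 6.5 foresees CR.

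**Step 4. Size for PFS.** Inputs: cohort of 45 (Protocol 3.1.3). Assumptions: w = 3 to 15 affected (not in the documents); the same true Week 24 PFS, S, in all; every PD by Week 24 counted; a share h of the affected subjects progression-free at Week 24 kept in the risk set by a later PD or an adequate scan at or after Week 24.

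Estimate = 1 − 45(1 − S) / [45 − (1 − h)·S·w]

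Worst case, h = 0:
- S = 0.70: w = 3 gives 1 − 13.5/42.9 = 0.685; w = 15 gives 1 − 13.5/34.5 = 0.609.
- S = 0.50: 1 − 22.5/43.5 = 0.483; 1 − 22.5/37.5 = 0.400.
- S = 0.80: 1 − 9/42.6 = 0.789; 1 − 9/33 = 0.727.

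Half retained, h = 0.5, S = 0.70: 1 − 13.5/43.95 = 0.693; 1 − 13.5/39.75 = 0.660.

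**Step 5. If an NE visit counts as missing.** The SAP does not say whether it does under the rule on 2 or more consecutive missing assessments. If so, a PD first recorded at Week 24 after NE at Weeks 8 and 16 is censored too. Late PDs are plausible because, without compelling evidence of progression, Protocol 6.20.7.7 says "all subjects should have at least 4 months of treatment before an assessment of PD is made". Keep h = 0 and S = 0.70:
- Half of affected PDs remain events: 1 − 13.05/42.45 = 0.693 (w = 3); 1 − 11.25/32.25 = 0.651 (w = 15).
- None remain: the estimate stays 0.70 but rests on 42 to 30 subjects, with SE √(0.21/42) = 0.071 to √(0.21/30) = 0.084, against √(0.21/45) = 0.068.

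**Step 6. Size for ORR, assuming a true 0.40.**
- Literal NE, no adequate scan in any affected subject: 0.40 × 42/45 = 0.373; 0.40 × 30/45 = 0.267.
- NE waived, with 25% to 75% of affected responders having a fall of 50% or more: 0.40 − 0.40 × 0.25 × 3/45 = 0.393; 0.40 − 0.40 × 0.75 × 15/45 = 0.300. This assumes no CR, VGPR, earlier MR or index lesion in any affected subject. If half had an earlier MR, the loss halves: 0.397 and 0.350.

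**The case against.** **Later scans rescue subjects.** Protocol 6.20.3 and Appendix 2 note i call for an End of Study tumor evaluation, and 6.5.1 requires CT at least every 6 months after Week 72, all without an LPL/WM exception. One non-NE scan at or after Week 24 keeps a progression-free subject in the Week 24 estimate. This stands, and it makes 0.685 to 0.609 a worst case. It does not remove the problem: 6.7 routes the End of Study assessment through 6.5, so the waiver may reach it, and a scan before Week 24 censors the subject at that scan.

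**The specific text governs.** The NE sentence in 6.20.7.1 speaks of radiological assessment, and a separate item gives LPL/WM an IgM route. That is a fair account of intent. But 6.20.7.8 addresses LPL/WM directly and adds a way to be NE without removing one.

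**The IRC charter may settle it.** The IRC's reads are primary and its charter is not among these documents. This is a reason to check the charter; it does not make the protocol and SAP consistent.

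**The category gap is arguable.** A reader might infer that a fall of 50% or more has no category at all. The documents do not force that. The SPD condition could be read as not applicable, giving PR, or the subject could be placed in SD because PR is not met. No text says the former, and under the latter a 60% fall is a non-response while a 30% fall is a response. The gap is also narrower than the unscanned group: a node just over 1.0 cm can be an index lesion although eligibility disease is 2.0 × 1.0 cm, and an earlier MR still counts in best response.

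**Limited reach.** The cohort has no futility rule, the study is exploratory and the report is synoptic. SAP 6.2.2.1 tabulates NE, MR and VGPR and lists IRC responses by subject, so the ORR effect would be partly visible. All of this stands and limits the weight of the point.

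**Conclusion.** The conflict is real on the text, and neither evident intent nor an unseen charter resolves it. Literally, an unscanned LPL/WM subject alive without a documented PD is censored on Day 1 and fails ORR. With NE waived and no index lesion, the PR rule cannot be met.

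The size is uncertain. With 3 to 15 of 45 affected and equal true rates, a true Week 24 PFS of 0.70 becomes 0.685 to 0.609 only if no affected subject progression-free at Week 24 has an End of Study scan, a post-Week-72 scan or a later PD. With half of them retained it is about 0.693 to 0.660, and other readings bring the bias toward zero.

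Two stronger inferences are not supported. A reader might take 0.609 as the expected result, or assume that every unscanned subject is lost from PFS; the later-scan provisions and counted PDs speak against both. A reader might also add the two ORR effects; they are alternatives, since the category gap arises only if NE is waived. Only the reported estimates of one cohort are affected.

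A minor, separate point: the protocol synopsis promises iNHL data by histology, but SAP Table 3-1 pools LPL/WM, SLL and MZL and SAP 6.3 does not declare this.

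**What to change.** Before database finalization:

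1. Reconcile Protocol 3.2, 6.5, 6.5.1, 6.12, 6.20.2, 6.20.3, 6.20.7.1, 6.20.7.8 and Appendix 2 notes h and i. For LPL/WM subjects without radiographic disease at baseline, state that the scheduled IgM, with marrow where required, is an adequate assessment that can yield a status other than NE.
2. In SAP Appendix 2, state whether an NE visit counts as missing under the rule on 2 or more missing assessments. Adequacy is already defined there by response status, so nothing else in that appendix needs to change.
3. Reconcile Protocol 6.20.7.2 to 6.20.7.4 with 6.5. Apply the SPD-decrease condition for LPL/WM PR only when index lesions exist at baseline, and say how the imaging conditions for CR and VGPR apply to unscanned subjects.
4. Confirm that the IRC charter uses the same rules.
5. Document the change as made after enrollment, and tabulate ORR under both the present and the clarified protocol wording.
6. Report LPL/WM, SLL and MZL separately, or declare the pooling in SAP 6.3.

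**Cost.** Wording only, with no new data collection. Some IRC responses may need re-derivation. The PR clarification comes late in an open-label study and can only raise ORR, which is why both versions should be shown. Histology columns would have small N; one line in SAP 6.3 is the cheaper alternative.

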6.20.7.9. No Disease

In a subject who does not have evidence of PD, the occurrence of the following condition indicates a response status of ND:

- No index disease noted at baseline or on-treatment.
- No non-index disease noted at baseline or on-treatment.
- Enlargement of the liver or spleen is absent both at baseline and on-treatment
- In a subject with LPL/WM, the additional requirement that serum monoclonal IgM protein as assessed by SPEP is absent at both baseline and on-study.

